4.1 Inclusion Criteria

Patients will be eligible for the study if all of the following criteria are met:

1. Sign and date the informed consent form approved by the IRB
2. ≥ 18 years of age
3. Demonstrate at least any 2 of the following signs in the same eye or a sign and symptom.
 - a) Conjunctival staining present ≥ 1 (out of possible score of 6 per eye)
 - b) Corneal staining present ≥ 2 (out of a possible score of 15 per eye)
 - c) Tear film break up time (TFBUT) ≤ 7 seconds
 - d) Schirmer's test ≥ 0 to ≤ 9 mm/5min
 - e) SLK pattern staining ≥ 1
 - f) Meiboscale grade ≥ 2
 - g) Validated Bulbar Redness ≥ 40
 - h) Demonstrate symptoms of dry eye disease OSDI score of at least ≥ 13 .
 - i) Demonstrate Symptom Intensity Assessment of ≥ 3 .
4. Patient reported dry eye-related ocular symptoms for at least 6 months before the Screening Visit and use or desire to use artificial tears on average 2 times per day in the 2 weeks preceding the screening visit
5. Intraocular pressure (IOP) ≥ 5 mmHg and ≤ 22 mmHg in each eye
6. Women of child-bearing potential must agree to use a reliable method of contraception during study participation and must demonstrate a negative pregnancy test at the Screening Visit
7. Be willing/able to return for all study visits and to follow instructions from the study investigator and his/her staff
8. Ocular Surface Wash Anti-Citrullinated Protein Antibody (ACPA) value of > 4.4 units in either eye at any time in the past.

4.2 Exclusion Criteria

Subjects will not be eligible for the study if any of the following criteria are met:

1. Allergic to IVIG or any similar products, or excipients of IVIG eye drops 4 mg/ml.
2. Use of contact lenses within the last 2-weeks prior to the baseline Visit.
3. Use of Allogenic serum or plasma eye drops within the last 2-weeks prior to the baseline Visit.
4. Unwilling to commit to no use of contact lenses for the duration of the study.
5. Pregnant or nursing/lactating
6. Participation in a study of an investigational drug or device within the 30 days preceding the Screening Visit
7. Current diagnosis of any of the following ocular conditions:
 - i) Acute allergic conjunctivitis
 - ii) Active infection (e.g. bacterial, viral, protozoan or fungal infection of the cornea, conjunctiva, lacrimal gland, lacrimal sac or eyelids)
 - iii) Active intraocular inflammation (e.g., retinitis, choroiditis, uveitis)
8. Ocular surgery (including cataract surgery), by patient report, within 3 months of Screening Visit
9. Previous LASIK surgery or any other corneal transplant surgery, by patient report.
10. Cognitive or psychiatric deficit that precludes informed consent or ability to perform
11. Vulnerable populations, such as neonates, pregnant women, children, prisoners, institutionalized individuals, or others who may be considered vulnerable populations.
12. Have active drug/alcohol dependence or abuse.
13. Corneal epithelial defect larger than 1 mm² in either eye.
14. Active ocular infection or ocular allergies.

Participants will be permitted to continue their chronic ocular treatments, including the use of artificial tears, ointments, prescription eye drops (Restasis, Xiidra, Steroids), eyelid massage, or warm compresses. Subjects will be asked to maintain their ocular treatments unchanged in frequency of use for the duration of the study. Subjects wearing contact lenses (Soft bandage contact lenses or PROSE lens) or using serum tears will be asked to discontinue contact lens wear or use of serum tears for 2-weeks prior to being enrolled (Baseline visit) and will be required to not wear contact lenses or use of serum tears for the duration of the study (until week 10 visit). All systemic medications will continue unchanged.

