1.8 Specific Agent in this Study

The primary agent used in this study is a commercial Intravenous immunoglobulins (IVIG) formulation (Flebogamma DIF 5%) that will be diluted in 0.9% saline to achieve 4 mg/ml (0.4%) IgG concentration, and dispensed as eye drops. Intravenous immunoglobulins (IVIG) are a therapeutic preparation of pooled normal human IgGs obtained from large numbers of healthy donors.

Flebogamma DIF 5% IVIG is an FDA-approved product available as 50 mg/ml an immune globulin intravenous (human) solution indicated in adults and pediatric patients 2 years of age and older for the treatment of primary immunodeficiency (PI), including the humoral immune defects in common variable immunodeficiency, x-linked agammaglobulinemia, severe combined immunodeficiency, and Wiskott-Aldrich syndrome. It is stable at room temperature for more than two years.

Flebogamma 5% DIF contains 5 g human normal immunoglobulin and 5 g D-sorbitol (as stabilizer) in 100 mL of water for injection, and ≤ 3 mg/mL polyethylene glycol. There is no preservative in the formulation. The pH of the solution ranges from 5 to 6 and the osmolality from 240 to 370 mOsm/L, which is within the normal physiological range.

From a safety perspective, IVIG eye drops would most closely resemble allogeneic unfractionated blood eye drops (serum or plasma). From an efficacy perspective, IVIG eye drops have the potential to significantly improve outcomes of autoimmune and inflammatory ocular surface disease, given the long shelf life at room temperature making storage & dispensing by pharmacies possible.

IgG at 4 mg/ml (0.4%) concentration (in the form of serum/plasma 50% eye drops) is routinely used to treat ocular surface diseases, however widespread use is limited because of short shelf life and limited number of blood processing compounding pharmacies. We propose to use IgG at a similar 4 mg/ml (0.4%) concentration (in the form of IVIG eye drops) to treat ocular surface diseases as this strategy offers significant advantages, chief amongst which is a long shelf life at room temperature that makes widespread dispensing possible.

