1.12 Dose Rationale and Risk/Benefits

Proposed dose: IVIG eye drops 4 mg/ml (0.4%) two times a day.

Rationale: Serum eye drops, compounded by diluting serum by 50% in normal saline, are routinely used for treating ocular surface diseases. The amount of IgG in undiluted serum is approximately 10 mg/ml, therefore 50% serum eye drops has approximately 5 mg/ml IgG, and serum eye drops are generally used four times a day. Since, at 50% dilution serum eye drops are effective in treating ocular surface diseases, we have proposed a similar dose of IgG in IVIG eye drops (4 mg/ml). In our in vitro experiments, we have determined 4 mg/ml IVIG to be non-toxic, as this dose, when added to medium of cultured epithelial cells for 24 hours, did not cause an increase in LDH concentration in the supernatant.

Also, it is generally accepted that IVIG should be given at a concentration that is at least 4 times the concentration of IgG at the application site. In ocular surface diseases, we have estimated IgG amount on the ocular surface to be approximately 0.5 mg/ml, therefore the IVIG dose should be at least 2 mg/ml to be effective. Taken together, our proposed dose of IVIG eye drops replicates the clinically in-use dose of IgG in serum tears, is non-toxic in vitro, and above the threshold required to be effective.

Adverse Effects of IVIG Treatment: To date, IVIG has been administered via systemic route only. Mild to moderate adverse reactions to high-dose IVIG therapy might be seen in nearly 30% of patients. Some of the common adverse reactions include fever, headache, chills, nausea, hypotension, and muscle cramps. Temporary cessation of the IVIG infusion, slow infusion, and use of general anti-inflammatory agents can control these events. Switching to SCIG is another viable alternative. Anaphylaxis can occur in IgA-deficient patients and use of low IgA-containing IVIG preparations is recommended in such cases. Other effects include meningeal inflammation and aseptic meningitis due to the release of inflammatory cytokines and neutrophil activation by IgG Abs within IVIG that mimic antineutrophil cytoplasmic Abs; intravascular hemolysis due to the presence of anti-A or anti-B isoagglutinins or less commonly anti-D or anti-K Abs; thromboembolism because of contamination of IVIG with clotting factors and formation of platelet-leukocyte aggregates; and renal complications due to osmotic injury that could be prevented by using non-sugarstabilized IVIG.

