4.4 Early Withdrawal of Subjects

4.4.1 When and How to Withdraw Subjects

Subjects have the right to withdraw from the study at any time, for any reason, without jeopardizing their medical care. Where possible, subjects will be followed for safety and encouraged to return for follow-up visits for any unresolved safety events.

The IRB and Investigator also have the right to withdraw subjects from the study for the following reasons: when continuation may jeopardize the health of the subject, protocol violations, adverse events or concurrent conditions, administrative or other reasons.

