5.1 Description

The study drug, IVIG-eye drops, will be compounded in the UIC Eye and Ear Infirmary (EEI) Pharmacy and supplied as a 4 mg/ml (0.4%) preservative free solution in single use vials for administration as topical eye drops. The control group will receive Normal saline eye drops as placebo.

Each subject will receive either IVIG-eye drops (study drug) or Normal saline (placebo) solution, as a single eye drop in each eye two times a day (BID) for eight weeks. Except for the first dose on Day1, subjects will self-administer the test medication eye drops at home.

Subjects will not be charged for the test medication in any way (neither the cost of the medication nor its dispensing cost).

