6.5.1 Visit 1 Screening

Day -21 to 0

After obtaining informed consent, the following assessments will be performed within fourteen days prior to the subject receiving the first dose of study medication:

- Demographic information including: birth date, gender, race or ethnic origin.
- Medical History including prior medication use and prior procedures: Medical history will be obtained by interviewing the subject and will include a review of the following systems: cardiovascular, dermatologic, gastrointestinal, genitourinary, musculoskeletal, neurologic and respiratory. An allergic history (including medications and food), substance abuse history (including alcohol) and a history of medication use (including prescription, OTC, and herbal products) during the past 30 days will also be completed.
- Ophthalmic and Dry Eye Disease history including: date when the Dry Eye Disease began, verification that the subject has had Dry Eye Disease for at least 6 months, medications used by the subject to treat Dry Eye Disease, previous procedures to treat Dry Eye Disease.

- Ophthalmic Examination (slit lamp examination, Ocular Surface Redness Score, Ocular Surface Disease Index, Lissamine Dye staining, and a Schirmer I test)
- Pregnancy test, if applicable. Women of reproductive age will be asked to use a method of birth control that is acceptable to the subject and the study doctor. This may include oral contraceptive pills, birth control implants/shots or patches, barrier methods or abstinence. Women of reproductive age will not be included in the study if they refuse to use any birth control measure, including abstinence.

Subjects currently treating DED with corticosteroids and/or Restasis will continue these treatments during the whole study. If patients are wearing contact lenses (Soft bandage contact lenses or PROSE lens) or using serum tears, they will be asked to discontinue contact lens wear or use of serum tears for 2-weeks prior to being enrolled (Baseline visit) and will be required to not wear contact lenses or use serum tears for the duration of the study (until week 10 visit). The study doctor will provide advice about decreasing DED symptoms with artificial tears, eyelid massage, or warm compresses.

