Evidence exists that the AE has an etiology other than the IVIG (e.g., preexisting medical condition, underlying disease, intercurrent illness, or concomitant medication); and/or the AE has no plausible temporal relationship to IVIG administration (e.g., cancer diagnosed 2 days after first dose of study drug)

Life-threatening: Any adverse drug experience in which the subject was at risk of death at the time of the event. It does not refer to an event which hypothetically might have caused death if it were more severe.

Expected adverse event: Expected adverse events are those adverse events that are listed or characterized in the Package Insert (P.I) or current Investigator Brochure (I.B).

Unexpected adverse event: Any adverse event, the specificity or severity of which is not consistent with the current Investigator's Brochure.

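### Section 4.2 leaves patients with known IgA deficiency eligible, although section 1.12 names them as at risk of anaphylaxis with (systemic) IVIG

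*Combined protocol and SAP*

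**What the plan says.** Section 4.2 lists 14 exclusions. The first covers hypersensitivity to the product: "Allergic to IVIG or any similar products, or excipients of IVIG eye drops 4 mg/ml". None of the others concerns immunoglobulin deficiency, and neither do the inclusion criteria in section 4.1.

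Section 1.12 reviews the adverse effects of IVIG. It sets the context with "To date, IVIG has been administered via systemic route only" and then states: "Anaphylaxis can occur in IgA-deficient patients and use of low IgA-containing IVIG preparations is recommended in such cases".

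On the product, section 1.8 says: "Flebogamma 5% DIF contains 5 g human normal immunoglobulin and 5 g D-sorbitol (as stabilizer) in 100 mL of water for injection". It adds a limit for polyethylene glycol and gives no IgA content. Section 5.4 allows Flebogamma or an equivalent preparation and sets no IgA limit for a substitute.

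The screening history in section 6.5.1 covers these body systems: "cardiovascular, dermatologic, gastrointestinal, genitourinary, musculoskeletal, neurologic and respiratory". It also takes medication and food allergies. The same section lets patients already followed in the investigator's clinic go to the baseline visit without formal screening. On dosing, section 5.1 says: "Except for the first dose on Day1, subjects will self-administer the test medication eye drops at home".

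**The concern.** The protocol identifies a group of patients, defined by a condition they already have, in whom the drug class can cause anaphylaxis. It then writes eligibility criteria that do not mention them. The allergy exclusion does not fill the gap, because an IgA-deficient patient never given IVIG would normally have no known allergy to it. The mitigation that section 1.12 names, a low-IgA product, is not written into the product sections either.

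What is at stake is subject safety. Efficacy inference is not affected. Section 2 makes safety and tolerability the main objective, and section 1.7 says IVIG has not been used as eye drops before, so no human topical data show that the risk is absent. Nearly all dosing takes place away from the clinic.

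**Working it through.** The plan gives no figure to reproduce. The check is whether any provision would keep out a patient with known IgA deficiency, followed by rough arithmetic on exposure.

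**Would such a patient be enrolled?**

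1. *Eligibility (4.1, 4.2).* No criterion names the condition. Exclusion 1 needs an existing allergy.
2. *Screening history (6.5.1).* Seven body systems plus medication and food allergy. A question on immune deficiency is not barred, but it is not required. Subjects who are not formally screened may not have this history taken for the study at all.
3. *Product (1.8, 5.4).* No IgA content or limit is stated, and substitution is allowed.
4. *Withdrawal (4.4.1).* The IRB or investigator may withdraw a subject "when continuation may jeopardize the health of the subject, protocol violations, adverse events or concurrent conditions, administrative or other reasons". This is discretionary and applies only after entry.
5. *Monitoring (5.6, 6.5.2).* A check for adverse effects follows the first dose. Subjects are withdrawn for presumed ocular allergic reaction, and the study stops if the incidence passes 20%. All of these act after exposure, and the withdrawal and stopping rules concern ocular events.

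Nothing in this chain stops the patient before the first dose.

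**Is IgA deficiency different from the other risks in 1.12?** That section links hemolysis to isoagglutinins and other antibodies in the product, thromboembolism to clotting-factor contamination and platelet-leukocyte aggregates, renal injury to osmotic load, and meningitis to cytokine release and antibodies within IVIG. Only the anaphylaxis risk is tied to a pre-existing patient condition, so only that one points directly to an eligibility item.

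**Unsupervised dosing** (5.2, 5.1)

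- Nominal doses: 2 per day × 56 days = 112.
- Given in the clinic: 1 (Day 1). At home: 112 − 1 = 111.
- Share at home: 111 / 112 = 99.1%.

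**Exposure** (1.8, 5.2; the drop volume is assumed to be 0.025 to 0.05 ml because the plan gives none)

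- Dilution: 50 mg/ml ÷ 4 mg/ml = 12.5-fold.
- Volume per day: 0.025 to 0.05 ml × 2 eyes × 2 doses = 0.1 to 0.2 ml.
- IgG per day: 0.1 to 0.2 ml × 4 mg/ml = 0.4 to 0.8 mg.
- IgA content is unknown. For each 1 microgram/ml of IgA in the undiluted product, the drops contain 1 / 12.5 = 0.08 microgram/ml, so the daily amount is 0.08 × 0.1 to 0.2 = 0.008 to 0.016 microgram.

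The exposure figures point to a small dose. They do not establish a safe threshold for a sensitised patient, and the documents give none. The 99.1% describes where doses are taken and is not a measure of risk.

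**The case against.** The strongest reply is that the plan does not contradict itself. Section 1.12 describes high-dose systemic therapy, and for IgA-deficient patients it advises a low-IgA product. It does not advise exclusion. If the study product is already low in IgA, that advice is met. The package insert and Investigator's Brochure, which section 8.1 relies on for expected events, may give the content. They were not available, and neither was a stretch of background text just before section 1.12.

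Exposure also looks low. Section 1.7 argues that the risk is no greater than with allogeneic serum drops already in use, and the mouse study in section 1.10 found no rise in human IgG in tissue or serum. The first exposure is the supervised one, followed by an adverse-effect check. A product limit would also protect undiagnosed patients, whom an exclusion cannot reach.

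Most of this is fair, and it keeps the point minor. It does not remove it. Even if the named product is low in IgA, section 5.4 lets another be used with no such requirement. The serum-drop comparison is put forward as an expectation, and neither it nor the mouse work addresses hypersensitivity in an IgA-deficient person. The monitoring provisions take effect only once the patient has been dosed.

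**Conclusion.** The point holds as an optional, low-cost improvement. As written, the plan would enrol a patient with known IgA deficiency and no previous reaction to IVIG, with neither an eligibility control nor a product control against a risk the protocol itself describes.

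The size cannot be quantified. The documents give no prevalence of IgA deficiency among candidates, no IgA content and no rate of reaction to topical use. The exposure estimate rests on the assumed drop volume and suggests a low absolute risk. The conclusion that no product control exists rests on the protocol text alone; an IgA figure in the package insert or Investigator's Brochure would further reduce the concern for the named product. Validity of the planned analyses is not in question.

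**What to change.** Add *known IgA deficiency* to the exclusions in section 4.2, identified by one history question at Visit 1, with no new laboratory test. For subjects who bypass formal screening under section 6.5.1, ask the question at consent or at Visit 2 before randomisation.

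The cost is one line in the protocol, one question on the case report form and, rarely, a lost candidate. The change protects diagnosed patients only. Sample size and statistical methods stay as they are.

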4.3 Subject Recruitment and Screening

Potential subjects will be recruited from the clinical practice of the investigator at the time of their routine eye examination visit. The clinical practice is located in the Illinois Eye and Ear Infirmary, Department of Ophthalmology and Visual Sciences, University of Illinois at Chicago (UIC). Subjects will include patients who have been diagnosed with DED in the investigator's eye clinic (cornea clinic or the comprehensive eye clinic), in the Illinois Eye and Ear Infirmary. Furthermore, these patients would include only those who have had an ACPA value of > 4.4 units in ocular surface washings of either eye at any time in the past. Patients diagnosed with DED, and willing to enter the study, may be referred to the PI's clinic by other ophthalmologists at UIC, as well as the ophthalmology departments at Loyola University Chicago, University of Chicago, RUSH University, Cook County Hospital, and Northwestern University. These centers will be provided with 'information sheets' to provide to subjects before they come to the PI's clinic. Although patients may be referred from these sites, no study procedures, including enrollment will be performed at any site, other than the PI's clinic in Illinois Eye and Ear Infirmary. All subjects will be screened, recruited, and will attend all study related visits only at the PI's clinic in Illinois Eye and Ear Infirmary.

Patients with Dry Eye Disease (with Schirmer's test ≥ 0 to ≤ 9 mm/5min and annoying or activity limiting visual symptoms) will be approached by a member of the research staff to determine if the subject might be interested in participating in a research study. If the subject is interested, the research staff member will describe the study. If the subject is willing to enter the study, the subject will be asked to review the study consent form, the PI will meet with the subject to review the form, the study will be discussed to confirm the subject's understanding of the study, and to answer any questions that the subject might have. Once the subject demonstrates understanding of the study and agrees to participate in the study, the subject will be asked to sign the informed consent form in the presence of the PI. Consent will be obtained prior to performing any screening tests to determine eligibility. Screening procedures include documentation of DED as well as other assessments as detailed in section 6.5.1. Eligible subjects will be enrolled in the study.

4.4 Early Withdrawal of Subjects

4.4.1 When and How to Withdraw Subjects

Subjects have the right to withdraw from the study at any time, for any reason, without jeopardizing their medical care. Where possible, subjects will be followed for safety and encouraged to return for follow-up visits for any unresolved safety events.

The IRB and Investigator also have the right to withdraw subjects from the study for the following reasons: when continuation may jeopardize the health of the subject, protocol violations, adverse events or concurrent conditions, administrative or other reasons.

4.4.2 Data Collection and Follow-up for Withdrawn Subjects

If a subject withdraws from the study prior to 8 weeks, the subject will be asked to complete the procedures outlined in the 10 week visit as well as the Test Substance Tolerance scale from 8 weeks, as soon as possible. Subjects who voluntarily withdraw from the study between 8 weeks and 10 weeks will be asked to complete procedures outlined in the 10 weeks visit as soon as possible. Subjects who are withdrawn due to adverse events will be followed at least until resolution or stabilization of the adverse event.

If the subject remains in the study for safety evaluation, follow-up visits will be scheduled according to the schedule of visits and procedures found in the synopsis.

5 Study Drug

